### Procedures

Participants will be randomly assigned to one of the following three groups: Yi Jin Bang, usual exercise therapy, or control group. Two experimental groups will do home-based Yi Jin Bang exercise and home-based exercise therapy for ten weeks, respectively. The control group will receive no treatment during the period of ten weeks. In addition, during the intervention, participants should not take any other physical therapy, exercise therapy, or medication on the shoulder.

# Yi Jin Bang Group

Each participant in this group will do a home-based Yi Jin Bang exercise program four times a week for ten consecutive weeks, which consists of ten minutes of warm-up, 18 minutes of Yi Jin Bang exercise (ten exercises), and ten minutes of cool-down. To learn how to conduct the home-based exercise session, each participant will be invited to one introductory session before starting the prescribed exercise program. Two experienced Yi Jin Bang instructors will lead the introductory session. Besides, in order to monitor participants' adherence and help them to conduct self-training, we will use the Zoom Meeting application. Zoom can capture and record participants movements through the webcam. During the introduction sessions, we will teach participants how to use Zoom. Furthermore, we will provide support for adherence to the home exercise sessions through telephone calls or e-mail every two weeks.

# Usual Exercise Therapy Group

Among exercise therapy in the treatment of SAPS, stretching and strengthening protocols are often used (Ludewig & Borstad, 2003). Therefore, participants in this group will do a standardized home-based stretching and strengthening exercise program four times per week for ten weeks, which is set up according to a previous study (McClure et al., 2004). This self-training program includes four stretching and seven strengthening exercises, which has been demonstrated that can be effective in reducing pain and improving function in patients with SAPS. For strengthening exercises, elastic bands will be used. To learn how to conduct the self-training program, each participant in this group will also be invited to one introductory session before starting the prescribed exercise training. Two certificated physiotherapists will lead the introductory session. In addition, a video demonstration clip will be given to each participant to provide a home reference, and the Zoom Meeting application will be used to help monitor the exercise. We will also provide support for adherence to the home self-training program through telephone calls or e-mail every two

weeks.

#### Waitlist Control Group

Participants in the waitlist control group will be informed that they will receive either Yi Jin Bang training or exercise therapy after ten weeks have passed. This will be done only for motivational reasons and not for evaluation.

#### Functional Disability

Functional disability will be measured using the SPADI. This is a self-reported questionnaire assessing pain and functional status, which consists of five questions regarding pain and eight questions regarding disability. Each question is scored from 0 to 10, and the total score ranges from 0 to 100. Greater scores represent higher levels of pain and disability. The SPADI has provided good psychometric with the test-retest reliability has been reported range from 0.84 to 0.91 (Roy et al., 2009).

#### Pain Intensity

Pain intensity will be measured on an 11 points numerical rating scale (Huskisson et al., 1976).

Participants will be asked to place a vertical mark on a horizontal line to indicate their current pain degree in rest and activity, where 0 for no pain and 10 for unbearable pain.

#### Flexibility

According to the method described by Norkin & White (2016), active flexion and abduction ROMs will be measured while the participant in standing position by a standard goniometer. The maximum ROM of three repetitions in each movement will be used for analyzing. Besides, back scratch test will measure participants' ROM by measuring the distance between the middle fingertip of the upper hand and the middle fingertip of the lower hand.

### Muscular Endurance

Muscular endurance will be measured using elastic bands. During the test, the participant will in standing position, with the test shoulder off the table and the arm perpendicular to the floor. The participant will be instructed to horizontally abduct his/her arm to 90 degrees at a cadence of 30 beats per minute. Repetitions will be performed until the participant is fatigued, indicated by one of the following conditions: the inability to hold the arm at the top of the arc for the required duration (1 second), compensation with elevation of entire upper torso, or verbal report of the inability to continue.

#### **Statistical Analysis**

All values will be reported as mean  $\pm$  SD. Two-way analysis of variance (ANOVA) with repeated measure (2 times × 3 groups) will be used to analyze differences at baseline and at ten-week post-intervention. Differences between the change within each group will be examined by one-way ANOVA. Post hoc tests will be used when necessary, to verify the pair-wise differences between means. The  $\alpha$  level of p < 0.05 will be considered statistically significant for all comparisons. All statistical procedures will be performed by SPSS software.

- Bang, M., & Deyle, G. (2000). Comparison of supervised exercise with and without manual physical therapy for patients with shoulder impingement syndrome. *The Journal of Orthopaedic and Sports Physical Therapy*, 30(3), 126-137.
- Desmeules, F. H., Côté, C., & Frémont, P. (2003). Therapeutic Exercise and Orthopedic Manual Therapy for Impingement Syndrome: A Systematic Review. *Clinical Journal* of Sport Medicine, 13(3), 176-182.
- Diercks, R., Bron, Dorrestijn, Meskers, Naber, De Ruiter., Van Der Woude. (2014). Guideline for diagnosis and treatment of subacromial pain syndrome: A multidisciplinary review by the Dutch Orthopaedic Association. *Acta Orthopaedica*, *85*(3), 314-322.
- Ginn, K., & Cohen, M. (2005). Exercise therapy for shoulder pain aimed at restoring neuromuscular control: a randomized comparative clinical trial. *Journal of Rehabilitation Medicine*, 37(2), 115-122.
- Greving, K., Dorrestijn, Winters, Groenhof, Van Der Meer, Stevens, & Diercks. (2012). Incidence, prevalence, and consultation rates of shoulder complaints in general practice. *Scandinavian Journal of Rheumatology*, *41*(2), 150-155.
  Effectiveness of physical therapy treatment of clearly defined subacromial pain: A systematic review of randomised controlled trials. *British Journal of Sports*

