# **Objectives**

To compare the effectiveness of ten weeks of home-based Yi Jin Bang exercise, versus home-based stretching and strengthening exercise, and versus waitlist control on pain, disability, flexibility, and muscular endurance in adults with SAPS. This study hypothesized that home-based Yi Jin Bang exercise and home-based stretching and strengthening exercise have similar effects in reducing pain and disability and improving flexibility and muscular endurance for individuals with SAPS.

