# Participants

This study will recruit 18-65 years old adults with symptoms of SAPS. Participants will be eligible if they meet all the following criteria: (1) aged 18 to 65 years old; (2) pain during overhead activities; (3) pain during active movements of the shoulder; (4) pain in the last three months; (5) Hawkins-Kennedy impingement test positive; (6) painful arc test positive; (7) infraspinatus muscle test positive. Participants will be excluded if they exhibited any of following criteria: (1) a history of fracture-dislocation of the shoulder; (2) full-thickness rotator cuff tear; (3) a history of shoulder surgery; (4) inflammatory of the vertebrae; (5) shoulder trauma in the last month; (6) any physical treatment for shoulder pain in the past month. Eligibility will be determined by two licensed physiotherapists through performing the clinical examination prior to entry into the study. Participants in this study will be recruited through mass email. Before the study, participants will be provided with consent forms, and then sign them. They will also be told that they can withdraw from the study at any time.

In terms of sample size, the effect size of the ROM exercise on the Shoulder Pain and Disability Index (SPDI) score found in a previous randomized control trial is adopted (Heron et al., 2017). Therefore, based on the estimation of sample size by G\*Power (effect size: 0.5;  $\alpha$ : 0.05; power: 0.80), a sample size of 14 individuals per group will be needed. Considering a 20% drop rate, we estimated that 18 participants per group will be needed.

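### The plan's test of the treatment effect is a change-score comparison that does not adjust for baseline; adjusting would usually narrow the intervals at almost no cost

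*Combined protocol and SAP*

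**What the plan says.** The analysis plan is one paragraph, headed Statistical Analysis. It names a two-way repeated-measures ANOVA (two times by three groups) that "will be used to analyze differences at baseline and at ten-week post-intervention". It then adds: "Differences between the change within each group will be examined by one-way ANOVA". Post hoc pairwise tests follow when needed, and the "level of p < 0.05 will be considered statistically significant for all comparisons". No covariate is named there or elsewhere, and no analysis population or missing-data rule is stated.

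The Participants section asks for 14 per group from an effect size of 0.5, alpha 0.05 and power 0.80, and then: "Considering a 20% drop rate, we estimated that 18 participants per group will be needed". The Objectives section hypothesises that "home-based Yi Jin Bang exercise and home-based stretching and strengthening exercise have similar effects in reducing pain and disability". Under Outcome Measures, disability (SPADI) is assessed only at baseline and ten weeks.

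**The concern.** The two ANOVAs look like two analyses, but for the question that matters they are one: do the arms differ in change from baseline? Subtracting baseline gives it a fixed weight of one. ANCOVA estimates that weight from the data. When baseline and ten-week values are only moderately correlated, a weight of one carries too much baseline noise into the comparison.

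What is at stake is precision, not validity. The trial is small, and one comparison of interest is between two active programmes expected to perform alike. For that comparison the width of the interval decides how informative the result is. The baseline value of every outcome is already collected, so the unused precision needs no new data.

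**Working it through.** **1. The plan's own sample size.** Read the effect size of 0.5 as Cohen's f in a three-group one-way ANOVA. With 14 per group, N = 42, the noncentrality is 42 × 0.5² = 10.5 on 2 and 39 degrees of freedom, and power is 0.803. With 13 per group it is 0.769. So 14 is the smallest n, and 14 / 0.8 = 17.5 rounds up to 18. Both stated figures reproduce.

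**2. The two ANOVAs give one test.** With two times, the within-person part of the repeated-measures model is the difference between the two values, so the group-by-time F equals the one-way F on change. On one simulated data set with 14 per group both were 3.3789. The two-way ANOVA also yields main effects, but these do not test the treatment difference in change. The time effect averages over arms. The group effect averages the pre-treatment value with the ten-week value.

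**3. Large-sample precision.** Let r be the baseline to ten-week correlation and k the baseline SD divided by the ten-week SD. Both are assumed. In units of the ten-week variance:
- change score: 1 + k² − 2rk
- baseline-adjusted: 1 − r²
- the first minus the second: (k − r)², which is never negative

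So in large samples the change score is never the more precise, and the two tie only when k = r.

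**4. With 14 completers in each of three arms.** Estimating the slope from 39 within-group degrees of freedom multiplies the adjusted variance, on average, by 1 + 1/(39 − 2) = 38/37. This assumes normal values and a common slope. The ratio of change-score to adjusted variance is then the large-sample ratio × 37/38. The last column is from 60,000 simulated trials.

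| r | k | Large sample | × 37/38 | Simulated |
|---|---|---|---|---|
| 0.3 | 1.0 | 1.54 | 1.50 | 1.50 |
| 0.5 | 1.0 | 1.33 | 1.30 | 1.30 |
| 0.7 | 1.0 | 1.18 | 1.15 | 1.14 |
| 0.5 | 0.7 | 1.05 | 1.03 | 1.02 |
| 0.5 | 1.2 | 1.65 | 1.61 | 1.61 |
| 0.7 | 0.7 | 1.00 | 0.97 | 0.975 |

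**5. Interval width at r = 0.5, k = 1.** The change-score standard error of a pairwise difference is √(2/14 × 1) = 0.378 SD. The adjusted one is √(2/14 × 0.75 × 38/37) = 0.332 SD. The simulated mean 95% half-widths, using the error pooled over three arms and no multiplicity correction, are 0.76 and 0.67 SD. To match the adjusted precision, a change-score analysis would need about 14 × 1.30 = 18.2 completers per arm.

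**6. Power at the plan's own effect size, 42 completers, k = 1.** The Participants section does not say whether 0.5 is on the change or the ten-week scale.
- Change scale: 0.803 for the change score; 0.943, 0.906 and 0.866 adjusted, at r = 0.3, 0.5 and 0.7.
- Ten-week scale: 0.651, 0.803 and 0.959 for the change score; 0.840, 0.906 and 0.980 adjusted.

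**7. Dropout, as a side check.** The 20% allowance is 18 × 0.2 = 3.6 per arm, or 10.8 of 54. People without a ten-week value have no change score and, unless values are imputed, enter neither ANOVA. For illustration, assume a true exercise versus waitlist effect of 0.50 SD, r = 0.5, k = 1, and dropout odds multiplied by 2.7 per SD.
- If dropout depends on baseline by one rule in both arms, the completer estimate is unbiased.
- If dropout depends on the change itself by one rule averaging 20%, the waitlist loses about 23% and the exercise arm about 17%, and the estimate is about 0.44.
- If 25% drop out of the waitlist and 15% of the exercise arm, driven by change, the estimate is 0.42 from change scores and 0.44 with baseline adjustment.

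These shifts are small against a standard error of about 0.38 SD.

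**The case against.** The strongest reply is that the plan contains no error here. Change-score analysis is unbiased under randomisation, the gain rests on r and k that nobody has stated, and on part of the range (k near r) there is essentially no gain. All of that stands. It does not defeat the change, because the trade is lopsided: the loss tried is under 3% in variance, while the gain is often 14% to 60%.

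Several stronger readings are tempting, and the documents do not support them.

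- **That the trial is underpowered.** The 14 per group reproduces as a one-way ANOVA with power 0.803, which is the planned test if the effect size is on the change scale. On the ten-week scale the change score could fall below 0.80 at low r, but the text does not say which scale applies.
- **That the adjusted interval would establish similarity.** No margin is stated, so neither 0.76 nor 0.67 SD is shown to be enough.
- **That leaving out dropouts will bias the result.** The documents do not show that dropout will differ by arm, and they suggest pulls in both directions. In the Yi Jin Bang arm, "we will provide support for adherence to the home exercise sessions through telephone calls or e-mail every two weeks", and the usual exercise arm has similar contact, but both also carry four sessions a week. The waitlist is promised later training, of which the plan says "This will be done only for motivational reasons and not for evaluation".
- **That equal dropout rates would remove the problem.** In the illustration, one shared rule is harmless when it acts on baseline but not when it acts on the change.
- **That imputation or a mixed model would recover the missing people.** For SPADI there are only two assessments, so someone who misses the second contributes baseline alone, which adds little about the group difference.

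**Conclusion.** The point holds as one of precision. The plan has one test of the treatment effect, and it ignores baseline except by subtraction. With 14 completers per arm, the change-score variance is about 1.14 to 1.5 times the adjusted variance for r from 0.7 down to 0.3 with k = 1. At r = 0.5 it is about 1.02 to 1.6 times for k from 0.7 to 1.2. It is about 0.97 times in the least favourable case tried (r = 0.7, k = 0.7). These figures assume r and k, normal outcomes and a common slope across arms. That the group-by-time test is the change-score test, and that the change score never wins in large samples, depends on none of the assumed values.

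This does not make the planned analysis invalid, the stated 14 and 18 per group wrong, or dropout bias established. The unstated handling of dropouts is a secondary matter of missing detail.

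**What to change.** In the Statistical Analysis section, make the main analysis of each outcome a comparison of ten-week values between the groups as randomised, adjusted for that outcome's baseline value (ANCOVA). Report pairwise differences with 95% confidence intervals. The one-way ANOVA on change can be kept as a secondary description.

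As a secondary addition, seek the ten-week assessment from everyone, including those who stop exercising, analyse them in the assigned group, and report dropout by arm. Any missing-data method that is added should be described as helping little for SPADI. Baseline adjustment should not be presented as a cure for dropout that depends on the unseen ten-week value.

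The cost is a few sentences, one degree of freedom and, at worst in the range tried, under 3% in variance. The analysis can be run in the SPSS already planned, and neither 14 nor 18 per group needs to rise. Following up those who stop exercising takes some extra effort but adds no visit.

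### Seven unranked outcomes are each tested at p < 0.05, with no primary outcome and no rule across outcomes, so a chance finding on at least one is likelier than 5% in most settings considered.

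*Combined protocol and SAP*

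**What the plan says.** The Objectives compare Yi Jin Bang with usual exercise and "versus waitlist control on pain, disability, flexibility, and muscular endurance in adults with SAPS". The four domains stand side by side. The hypothesis is that the two exercise programmes "have similar effects in reducing pain and disability and improving flexibility and muscular endurance".

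The Outcome Measures section turns these domains into seven analysable variables: SPADI total (Functional Disability); pain at rest and pain in activity (Pain Intensity); flexion range of motion, abduction range of motion and back scratch distance (Flexibility); and repetitions to fatigue (Muscular Endurance). None is called primary, secondary or exploratory.

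SPADI has one further role. The sample-size paragraph under Participants adopts "the effect size of the ROM exercise on the Shoulder Pain and Disability Index (SPDI) score found in a previous randomized control trial" and concludes that "a sample size of 14 individuals per group will be needed". The analysis section does not single it out.

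Under Statistical Analysis, the arms are compared on change from baseline: "Differences between the change within each group will be examined by one-way ANOVA". On how pairs of arms are then compared, the plan offers one sentence: "Post hoc tests will be used when necessary, to verify the pair-wise differences between means". The post hoc procedure is not named. A single threshold covers everything, in that a "level of p < 0.05 will be considered statistically significant for all comparisons". There is no hierarchy, adjustment or other decision rule across outcomes.

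**The concern.** The 0.05 level limits error for one test. Nothing limits it over the set of seven, and nothing says which outcome decides the trial.

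Three situations matter. First, if neither programme does anything, each of the seven three-group tests is a separate chance of a positive finding. Second, both programmes may work equally well. This is closest to the plan's own expectation, since the comparator is described as one "which has been demonstrated that can be effective in reducing pain and improving function in patients with SAPS". The waitlist arm then makes the three-group test significant often, so requiring that test first gives little protection to the comparison between the exercise arms. A chance difference on one outcome would count against the hypothesis of similar effects, and no rule weighs it against the other six. Third, usual exercise may work while Yi Jin Bang does not. A chance result on any one outcome could then be presented as a benefit of Yi Jin Bang over waitlist.

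**Working it through.** **The plan's own figure.** Inputs from Participants: effect size 0.5, alpha 0.05, power 0.80, three groups, 20% dropout. For a one-way ANOVA with Cohen's f = 0.5, the noncentrality is 3n × 0.5². Power is 76.9% at n = 13 and 80.3% at n = 14, so 14 is reproduced, and 14/0.8 = 17.5 rounds up to 18. The metric of the 0.5 is not stated; that it is f is inferred from this match. A two-group comparison with a standardised difference of 0.5 would need 63 per group.

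**What f = 0.5 implies.** If two equal arms both lie δ SD above waitlist, f = δ√2/3. Then f = 0.5 gives δ = 0.5 × 3/√2 = 1.06 SD, and δ = 0.5 SD gives f = 0.236. Both values of δ are used below.

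**Upper bound.** For seven independent tests at 0.05 with no true differences, 1 − 0.95⁷ = 30.2%.

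**Correlated outcomes.** The documents give no correlations between outcomes, so 0, 0.5, 0.7 and 0.9 are assumed. The simulation drew equally correlated normal change scores on seven outcomes, with 14 per group. Each outcome had a three-group F test at 0.05. Pairwise contrasts used the pooled error (3 × 14 − 3 = 39 df) and were made only after a significant F test. The table gives the percentage of trials with at least one false finding.

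| Situation | Post hoc test | r = 0 | r = 0.5 | r = 0.7 | r = 0.9 |
|---|---|---|---|---|---|
| No true differences: any significant F | not relevant | 30 | 24 | 19 | 12 |
| Exercise arms equal, 1.06 SD above waitlist: they differ | unadjusted | 30 | 23 | 18 | 11 |
| Same | Tukey | 13 | 10 | 8 | 5 |
| Same | Bonferroni | 11 | 9 | 7 | 4 |
| Exercise arms equal, 0.5 SD above waitlist: they differ | unadjusted | 24 | 19 | 15 | 9 |
| Usual exercise 1.06 SD above waitlist, Yi Jin Bang equal to waitlist: Yi Jin Bang better than waitlist | unadjusted | 16 | 12 | 9 | 6 |
| Same, usual exercise 0.5 SD above waitlist | unadjusted | 13 | 9 | 7 | 5 |

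Tukey and Bonferroni give nearly the same figures for the 0.5 SD version of the second situation. They bring the third situation down to about 2-7%.

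**Fewer outcomes.** Counting one measure per domain (four), the first row becomes 19, 16, 14 and 10%, and the second row 18, 15, 13 and 9%.

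**SPADI alone as primary.** The three-group error is 5%. With unadjusted contrasts, a false difference between equal exercise arms occurs in 2.7% of trials if waitlist is no worse, 3.8% if it is 0.5 SD worse and 5.0% if it is 1.06 SD worse.

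**Splitting alpha instead.** Testing all seven at 0.05/7 = 0.00714 also holds a false difference between the exercise arms to at most 4.9%. At f = 0.5, however, power per outcome falls to 52% with 14 per group (69% with 18), and 80% power needs 22 per group (28 enrolled).

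**The case against.** SPADI sizes the trial, so a reader may take it as the implied primary outcome. That is a sensible guess, but the text borrows only its effect size and the analysis gives it no role. If it is meant as primary, one sentence settles the matter.

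A reader might also infer that about 9-30% is simply the false-difference rate between the exercise arms. The documents do not support that without a condition: it requires unadjusted contrasts. The 0.05 sentence allows that reading, but it also fits adjusted p-values from Tukey or Bonferroni, and then the range is about 4-13%. This part of the objection stands. It does not touch the three-group tests, whose 12-30% is the same for any post hoc method, and an adjustment over pairs of arms is not one over outcomes.

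The 30% end needs uncorrelated outcomes. That is hard to defend when SPADI itself contains pain items and three of the measures assess flexibility. At correlations of 0.5 to 0.9 the unadjusted figure for equal exercise arms is 9-23%.

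Finally, a chance difference works against the hypothesis of similar effects. A reader might infer that the multiplicity produces false claims of similarity; it does not. The damage is a spurious difference, or a spurious benefit over waitlist, that the plan has no rule for weighing.

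**Conclusion.** The gap is real and worth closing. Seven unranked measures are each tested at 0.05, and nothing says which one decides or how the results combine.

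With 14 per group and assumed correlations of 0 to 0.9:

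- At least one false three-group result under no effect: about 12-30%.
- A false difference between two equally effective exercise arms: about 9-30% with unadjusted contrasts, about 4-13% with Tukey or Bonferroni.
- A false Yi Jin Bang benefit over waitlist when only usual exercise works: about 5-16% unadjusted, about 2-7% adjusted.

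The omission is certain. The sizes are conditional on the correlations, the effects over waitlist, the post hoc method and the count of seven, which comes from the outcome descriptions and is not stated in the plan. At the lower end of the adjusted ranges the error is no more than 5%, so it would be wrong to say that it is inflated under every reading. Even there, no outcome has been named to decide the trial.

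**What to change.** Before outcome data are seen, name SPADI total score change at ten weeks as the single primary outcome. Test it with the three-group comparison already planned, at 0.05, and make pairwise claims only if that test is significant. Label the other six measures secondary and report them with 95% confidence intervals as supportive. If the sponsor wants confirmatory claims on them, test them after SPADI, in a pre-stated order or with Holm's procedure.

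This takes a few sentences and no extra participants. The 80% power for SPADI at 14 per group is unchanged if 0.5 is Cohen's f. If it instead meant each exercise arm 0.5 SD better than waitlist, power is 24%, and naming a primary outcome does not alter that either. The price is that results on pain ratings, flexibility and endurance, which the Objectives list on a par with disability, are claimed less strongly.
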